Note: Participants with nonalcoholic fatty liver disease are eligible to participate in this trial if their ALT level is $< 3.0 \times$ ULN for the reference range

- [16] Have an estimated glomerular filtration rate $< 30 \text{ mL/min/1.73 m}^2$, calculated by Chronic Kidney Disease-Epidemiology as determined by central laboratory at Visit 1
- [17] Have evidence of a significant, uncontrolled endocrine abnormality (for example, thyrotoxicosis or adrenal crises), in the opinion of the investigator
- [18] Have family or personal history of medullary thyroid carcinoma (MTC) or multiple endocrine neoplasia syndrome type 2 (MEN2)
- [19] Have a serum calcitonin level of $\geq 35 \text{ ng/L}$, as determined by central laboratory at Visit 1
- [20] Known or suspected hypersensitivity to trial product(s) or related products
- [21] Have evidence of a significant, active autoimmune abnormality (for example, lupus or rheumatoid arthritis) that, in the opinion of the investigator, is likely to require concurrent treatment with systemic glucocorticoids in the next 12 months
- [22] Have had a transplanted organ (corneal transplants [keratoplasty] allowed) or awaiting an organ transplant
- [23] Have a history of an active or untreated malignancy or are in remission from a clinically significant malignancy for less than 5 years. Exceptions for this criterion are:
 - basal or squamous cell skin cancer
 - *in situ* carcinomas of the cervix, and
 - *in situ* or grade 1 (for example, Gleason 6 or lower) prostate cancer
- [24] Have a history of any other condition (such as known drug, alcohol abuse, or psychiatric disorder) that, in the opinion of the investigator, may preclude the participant from following and completing the protocol
- [25] Have any hematological condition that may interfere with HbA1c measurement (for example, hemolytic anemias, sickle cell disease)

Prior/Concomitant Therapy

- [26] Use of insulin 1 year preceding Visit 1 and between Visit 1 and Visit 3; use of any antihyperglycemic medication 90 days preceding Visit 1 and between Visit 1 and Visit 3.

Note: An exception is for the use of insulin for gestational diabetes or short-term use (≤ 14 days) for certain clinical situations such as acute illness, hospitalization, or elective surgery.

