7.1.1. Liver Chemistry Stopping Criteria

Discontinuation due to a hepatic event or liver test abnormality

Participants who are discontinued from study intervention due to a hepatic event or liver test abnormality should have additional hepatic safety data collected via CRF.

The study intervention should be **interrupted** and close hepatic monitoring initiated (Section 10.5) if one or more of these conditions occur:

| Elevation | Exception |
|---|--|
| ALT or AST $>8 \times$ ULN | |
| ALT or AST $>5 \times$ ULN for more than 2 weeks | |
| ALT or AST $>3 \times$ ULN and either TBL $>2 \times$ ULN or INR >1.5 | For participants with Gilbert's syndrome: If baseline direct bilirubin is >0.5 mg/dL, then doubling of direct bilirubin should be used for drug interruption decisions rather than TBL $>2 \times$ ULN. |

| | |
|---|---|
| ALT or AST $>3 \times$ ULN with the appearance of fatigue, nausea, vomiting, right upper quadrant pain or tenderness, fever, rash, and/or eosinophilia ($>5\%$) | |
| ALP $>3 \times$ ULN, when the source of increased ALP is the liver | |
| ALP $>2.5 \times$ ULN and TBL $>2 \times$ ULN | For participants with Gilbert's syndrome: If baseline direct bilirubin is >0.5 mg/dL then doubling of direct bilirubin should be used for drug interruption decisions rather than TBL $>2 \times$ ULN. |
| ALP $>2.5 \times$ ULN with the appearance of fatigue, nausea, vomiting, right upper quadrant pain or tenderness, fever, rash, and/or eosinophilia ($>5\%$) | |

Source: FDA Guidance for Industry: Drug-Induced Liver Injury: Premarketing Clinical Evaluation, July 2009 and other consensus guidelines, with minor modifications

Abbreviations: ALT = alanine aminotransferase; AST = aspartate aminotransferase; ALP = alkaline phosphatase; INR = international normalized ratio; TBL = total bilirubin; ULN = upper limit of normal.

Resuming study intervention after elevated liver tests

Resumption of the study intervention can be considered only in consultation with the Lilly-designated medical monitor and only if the liver test results return to baseline and if a self-limited non-drug etiology is identified. Otherwise, the study intervention should be discontinued.

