8.2.7.1. Hepatic Safety Monitoring

Close hepatic monitoring

Initiating laboratory and clinical monitoring for abnormal liver laboratory test results

Laboratory tests, including ALT, AST, ALP, TBL, direct bilirubin (D. Bil), gamma-glutamyltransferase (GGT), and creatine kinase (CK), should be repeated within 48 to 72 hours to confirm the abnormality and to determine if it is increasing or decreasing, if one or more of these conditions occur:

| | |
|--|--|
| If a participant with baseline results of... | develops the following elevations: |
| ALT or AST $<1.5 \times$ ULN | ALT or AST $\geq 3 \times$ ULN |
| ALP $<1.5 \times$ ULN | ALP $\geq 2 \times$ ULN |
| TBL $<1.5 \times$ ULN | TBL $\geq 2 \times$ ULN (except for patients with Gilbert's syndrome) |
| ALT or AST $\geq 1.5 \times$ ULN | ALT or AST $\geq 2 \times$ baseline |
| ALP $\geq 1.5 \times$ ULN | ALP $\geq 2 \times$ baseline |
| TBL $\geq 1.5 \times$ ULN | TBL $\geq 1.5 \times$ baseline (except for patients with Gilbert's syndrome) |

Abbreviations: ALP = alkaline phosphatase; ALT = alanine aminotransferase; AST = aspartate aminotransferase; TBL = total bilirubin; ULN = upper limit of normal.

What to do if the abnormal condition persists or worsens

If the abnormality persists or worsens, clinical and laboratory monitoring, and evaluation for possible causes of abnormal liver tests should be initiated by the investigator in consultation with the Lilly-designated medical monitor. At a minimum, this evaluation should include physical examination and a thorough medical history, including symptoms, recent illnesses (for example, heart failure, systemic infection, hypotension, or seizures), recent travel, history of concomitant medications (including OTC), herbal and dietary supplements, history of alcohol drinking and other substance abuse.

Frequency of monitoring

Initially, monitoring of symptoms and hepatic biochemical tests should be done at a frequency of 1 to 3 times weekly, based on the participant's clinical condition and hepatic biochemical tests.

Subsequently, the frequency of monitoring may be lowered to once every 1 to 2 weeks, if the participant's clinical condition and lab results stabilize.

Monitoring of ALT, AST, ALP, and TBL should continue until levels normalize or return to approximate baseline levels.

Comprehensive hepatic evaluation

When to perform a comprehensive evaluation

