A comprehensive evaluation (Section 10.5 Appendix 5) should be performed to search for possible causes of liver injury if one or more of these conditions occur:

| If a participant with baseline results of... | develops the following elevations: |
|--|---|
| ALT or AST $<1.5 \times$ ULN | ALT or AST $\geq 3 \times$ ULN with hepatic signs/symptoms ^a , or ALT or AST $\geq 5 \times$ ULN |
| ALP $<1.5 \times$ ULN | ALP $\geq 3 \times$ ULN |
| TBL $<1.5 \times$ ULN | TBL $\geq 2 \times$ ULN (except for patients with Gilbert's syndrome) |
| ALT or AST $\geq 1.5 \times$ ULN | ALT or AST $\geq 2 \times$ baseline with hepatic signs/symptoms ^a , or ALT or AST $\geq 3 \times$ baseline |
| ALP $\geq 1.5 \times$ ULN | ALP $\geq 2 \times$ baseline |
| TBL $\geq 1.5 \times$ ULN | TBL $\geq 2 \times$ baseline (except for patients with Gilbert's syndrome) |

Abbreviations: ALP = alkaline phosphatase; ALT = alanine aminotransferase; AST = aspartate aminotransferase; TBL = total bilirubin level; ULN = upper limit of normal.

^a Hepatic signs/symptoms are severe fatigue, nausea, vomiting, right upper quadrant abdominal pain, fever, rash, and/or eosinophilia $>5\%$.

What a comprehensive evaluation should include

At a minimum, this evaluation should include physical examination and a thorough medical history, as outlined above, as well as tests for PT-INR; tests for viral hepatitis A, B, C, or E; tests for autoimmune hepatitis; and an abdominal imaging study (for example, ultrasound or computed tomography [CT] scan).

Based on the patient's history and initial results, further testing should be considered in consultation with the Lilly-designated medical monitor, including tests for hepatitis D virus, cytomegalovirus, Epstein-Barr virus, acetaminophen levels, acetaminophen protein adducts, urine toxicology screen, Wilson's disease, blood alcohol levels, urinary ethyl glucuronide, and blood phosphatidylethanol. Based on the circumstances and the investigator's assessment of the participant's clinical condition, the investigator should consider referring the participant for a hepatologist or gastroenterologist consultation, magnetic resonance cholangiopancreatography, endoscopic retrograde cholangiopancreatography, cardiac echocardiogram, or a liver biopsy.

Additional hepatic data collection (hepatic safety CRF) in study participants who have abnormal liver tests during the study

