10.2. Appendix 2: Clinical Laboratory Tests

- The tests detailed in the table below will be performed by the central laboratory.
- Local laboratory results are only required in the event that the central laboratory results are not available in time for either study intervention administration and/or response evaluation. If a local sample is required, it is important that the sample for central analysis is obtained at the same time. Additionally, if the local laboratory results are used to make either a study intervention decision or response evaluation, the results must be recorded.
- In circumstances where the sponsor approves local laboratory testing in lieu of central laboratory testing (in the table below), the local laboratory must be qualified in accordance with applicable local regulations.
- Protocol-specific requirements for inclusion or exclusion of participants are detailed in Section 5 of the protocol.
- Additional tests may be performed at any time during the study as determined necessary by the investigator or required by local regulations.
- Investigators must document their review of the laboratory safety results.

Laboratory/analyte results that could unblind the study will not be reported to investigative sites or other blinded personnel until the study has been unblinded.

| Clinical Laboratory Tests | Laboratory Name | Comments |
|---|--|--|
| Hematology^a | Labcorp Pharmaceutical Research and Development (Shanghai) Co., Ltd. | |
| Hemoglobin | | |
| Hematocrit | | |
| Erythrocyte count (RBCs) | | |
| Mean cell volume | | |
| Mean cell hemoglobin | | |
| Mean cell hemoglobin concentration | | |
| Leukocytes (WBCs) | | |
| Differential | | |
| Absolutes Count of: | | |
| Neutrophils, | | |
| Lymphocytes | | |
| Monocytes | | |
| Eosinophils | | |
| Basophils | | |
| Platelets | | |
| Cell morphology (RBCs and WBCs), if indicated | | |
| Clinical Chemistry | | Assayed by Lilly-designated laboratory |
| Sodium | | |
| Potassium | | |

| Clinical Laboratory Tests | Laboratory Name | Comments |
|------------------------------|-----------------|--|
| Chloride | | |
| Bicarbonate | | |
| Total bilirubin | | |
| Direct bilirubin | | |
| ALP | | |
| ALT | | |
| AST | | |
| BUN | | |
| Creatinine | | |
| CK | | |
| Uric acid | | |
| Albumin | | |
| Calcium | | |
| Glucose | | |
| Lipid Panel | | Assayed by Lilly designated laboratory. |
| Cholesterol | | |
| Triglycerides | | |
| HDL-C | | |

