10.4.2.2. Male

The table below describes contraception guidance for all men.

| Topic | Guidance |
|---|--|
| For all men | should refrain from sperm donation for the duration of the study and for 5 half-lives of study intervention, plus 90 days, corresponding 120 days (4 months) after the last dose of the study intervention. |
| Contraception for men with partners of childbearing potential | 
 • either remain abstinent (if this is their preferred and usual lifestyle), or • must use condoms during intercourse for the duration of the study, and • for 120 days (4 months) after the last dose of the study intervention. |
| Contraception for men in exclusively same sex relationships, as their preferred and usual lifestyle | Are not required to use contraception |

Examples of highly effective, effective and unacceptable methods of contraception can be found in Section [10.4.2.1](#).

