10.5. Appendix 5: Liver Safety: Suggested Actions and Follow-up Assessments

Hepatic Evaluation Testing

See Section 8.2.7.1 for guidance on appropriate test selection.

The Lilly-designated central laboratory should complete the analysis of all selected testing except for testing listed in the investigator-designated local laboratory table. The central laboratory will report results if a validated test or calculation is available.

In circumstances where required in accordance with local regulations, local laboratory testing may be performed in lieu of Lilly-designated central laboratory testing (in the table below).

Local testing may be performed *in addition to central testing* when necessary for immediate participant management.

The local laboratory must be qualified in accordance with applicable local regulations.

| Tests assayed by Lilly-designated central laboratory | |
|--|--|
| Hepatic Hematology Panel ^a | Hepatitis A virus (HAV) testing: |
| Hemoglobin | HAV total antibody |
| Hematocrit | HAV IgM antibody |
| Erythrocytes (RBCs - red blood cells) | Hepatitis B virus (HBV) testing: |
| Leukocytes (WBCs - white blood cells) | Hepatitis B surface antigen (HBsAg) |
| Differential: | Hepatitis B surface antibody (anti-HBs) |
| Neutrophils, segmented | Hepatitis B core total antibody (anti-HBc) |
| Lymphocytes | Hepatitis B core IgM antibody |
| Monocytes | HBV DNA ^b |
| Basophils | Hepatitis C virus (HCV) testing: |
| Eosinophils | HCV antibody |
| Platelets | HCV RNA ^b |
| Cell morphology (RBC and WBC) | Hepatitis D virus (HDV) testing: |
| Hepatic Clinical Chemistry Panel | HDV antibody |
| Total bilirubin | Hepatitis E virus (HEV) testing: |
| Direct bilirubin | HEV IgG antibody |
| Alkaline phosphatase (ALP) | HEV IgM antibody |
| Alanine aminotransferase (ALT) | HEV RNA ^b |
| Aspartate aminotransferase (AST) | Anti-nuclear antibody (ANA) |
| Gamma-glutamyl transferase (GGT) | Anti-smooth muscle antibody (ASMA) ^c |
| Creatine kinase (CK) | Anti-actin antibody ^d |
| Hepatic Coagulation Panel | Immunoglobulin IgA (quantitative) |
| Prothrombin time, INR (PT-INR) | Immunoglobulin IgG (quantitative) |
| Urine Chemistry | Immunoglobulin IgM (quantitative) |
| Drug screen | Epstein-Barr virus (EBV) testing: |
| Haptoglobin | EBV antibody |

| Tests assayed ONLY by investigator-designated local laboratory | |
|--|--|
| Acetaminophen | Cytomegalovirus (CMV) testing: |
| Acetaminophen protein adducts | CMV antibody |

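### The Section 7.1.1 rule that interrupts drug at ALT or AST >3×ULN with INR >1.5 relies on a test the protocol does not require at that threshold

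*Protocol*

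**What the plan says.** **The rule.** The table in Protocol Section 7.1.1 lists the liver findings at which study intervention should be interrupted. One row combines ALT or AST >3×ULN with either TBL >2 × "ULN or INR >1.5". INR is an alternative to bilirubin there, so it can decide by itself.

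**The tests.** Section 8.2.7.1 sets the laboratory work-up in steps.
- Close monitoring: "Laboratory tests, including ALT, AST, ALP, TBL, direct bilirubin (D. Bil), gamma-glutamyltransferase (GGT), and creatine kinase (CK), should be repeated" within 48 to 72 hours. For baseline ALT/AST <1.5×ULN the trigger is ≥3×ULN; for higher baselines it is ≥2 times baseline.
- If the abnormality persists or worsens, causes are evaluated in consultation with the medical monitor: "At a minimum, this evaluation should include physical examination and a thorough medical history, including symptoms, recent illnesses". Continued monitoring covers ALT, AST, ALP and TBL.
- The comprehensive evaluation is where INR first becomes mandatory: examination and history "as well as tests for PT-INR; tests for viral hepatitis A, B, C, or E".

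**Elsewhere.** The Schedule of Activities (Section 1.3) and the test list in Section 10.2 (Appendix 2) contain no coagulation test. Section 10.5 (Appendix 5) offers PT-INR in its Hepatic Coagulation Panel but sets no trigger: "See Section 8.2.7.1 for guidance on appropriate test selection". Section 10.2 also states: "Additional tests may be performed at any time during the study as determined necessary by the investigator".

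**The concern.** A stopping rule works only if its inputs are collected when it applies. A site that follows the listed panels exactly will have ALT, AST, ALP and bilirubin for a participant just above 3×ULN, but no INR. It cannot then tell whether the INR limb of 7.1.1 is met. An isolated INR rise with normal bilirubin and no symptoms would be missed unless someone chose to look for it.

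The stake is participant safety. A participant who meets a written interruption criterion could stay on weekly injections because the criterion was never evaluated. No efficacy or safety analysis in the SAP is affected.

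**Working it through.** The check is a comparison of thresholds. The inputs are the 7.1.1 interruption table, the two trigger tables in 8.2.7.1, and the entry limits in exclusion criterion 15 (Section 5.2).

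**1. Main case: baseline ALT/AST <1.5×ULN, no symptoms, ALT/AST >3 to <5×ULN, TBL <2×ULN, ALP <3×ULN.** Each row of 7.1.1 in turn:

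| 7.1.1 ground | Can it apply? |
|---|---|
| ALT or AST >8×ULN | No, below 5 |
| ALT or AST >5×ULN for more than 2 weeks | No, below 5 |
| ALT or AST >3×ULN with TBL >2×ULN | No, TBL <2 |
| ALT or AST >3×ULN with INR >1.5 | **Yes, if INR is known** |
| ALT or AST >3×ULN with listed symptoms | No, asymptomatic |
| ALP >3×ULN of liver origin | No, ALP <3 |
| ALP >2.5×ULN with TBL >2×ULN | No, TBL <2 |
| ALP >2.5×ULN with symptoms | No, asymptomatic |

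The comprehensive evaluation, and with it PT-INR, is required at ALT/AST ≥5×ULN, at ≥3×ULN with hepatic signs or symptoms, at TBL ≥2×ULN, or at ALP ≥3×ULN. None of these holds in the main case, so no INR is required.

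In the neighbouring cases INR is required, but drug is usually interrupted already on another row (symptoms, TBL >2×ULN, hepatic ALP >3×ULN). The exceptions are values exactly on a boundary, Gilbert's syndrome and ALP of non-hepatic origin.

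**2. Higher baselines.** Criterion 15 admits ALT and AST up to <3×ULN. Its note reads "Participants with nonalcoholic fatty liver disease are eligible to participate in this trial if their ALT level is" below 3×ULN, so baselines of 1.5 to <3×ULN can occur. For these the repeat trigger is 2 × baseline and the asymptomatic comprehensive trigger is 3 × baseline. In ×ULN, with no symptoms, TBL <2 and ALP below its triggers:

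| Baseline | Repeat panel from | INR limb applies from | PT-INR first required | Other ALT/AST limbs inside the gap |
|---|---|---|---|---|
| <1.5 | 3.0 | >3 | 5.0 | none |
| 1.5 | 3.0 | >3 | 3 × 1.5 = 4.5 | none |
| 2.0 | 4.0 | >3 | 3 × 2.0 = 6.0 | >5 for more than 2 weeks |
| 2.5 | 5.0 | >3 | 3 × 2.5 = 7.5 | >5 for more than 2 weeks |
| 2.9 | 5.8 | >3 | 3 × 2.9 = 8.7 | >5 for more than 2 weeks; >8 |

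The gap extends above 5×ULN once baseline exceeds 5/3 = 1.67×ULN. Above a baseline of 8/3 = 2.67×ULN, the >8×ULN limb interrupts before any INR is required.

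**3. How many participants.** The documents give no rate. If 0.5% to 3% of the 200 participants entered the main band (an assumption), that would be 200 × 0.005 = 1 to 200 × 0.03 = 6 people. The number who also had INR >1.5 would be smaller and cannot be derived from the documents.

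**The case against.** The strongest reply is that the protocol leaves ample room to act.
- The repeat list is introduced as inclusive, and examination and history are a floor.
- Section 10.2 allows extra tests, and Section 10.5 supplies the INR assay and permits local testing for immediate management.
- Section 7.1 lets the investigator discontinue drug for a clinically significant laboratory value, and Section 7.1.2 allows temporary interruption.
- Section 8 calls for immediate safety concerns to be raised with the sponsor.
- In the band, liver tests are repeated within 48 to 72 hours. If the abnormality persists, they are followed 1 to 3 times weekly at first, with the medical monitor involved.
- Nausea and vomiting are common on this drug, and at >3×ULN either one triggers interruption without an INR.

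Most of this stands, and it limits the point. A reader might infer that dosing has to continue in the band until something worsens. The documents do not support that, because discretionary stopping is always open. What survives is narrower: permission to test is not a requirement to test, and a rule that names INR should not depend on whether someone thinks to order it. The reference in 7.1.1 to Section 10.5 does not help, because that monitoring begins once a condition has been met and so cannot supply the INR that defines the condition.

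Two other stronger readings also fail. INR is the sole ground only up to 5×ULN; at higher baselines the >5×ULN-for-more-than-2-weeks and >8×ULN limbs also apply. And the assumed rates in step 3 give a chance of 1 − (1 − p)^200, or 63% to 99.8%, that at least one participant enters the band. That is not a chance of harm, which also needs INR >1.5 with TBL <2×ULN and no symptoms.

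**Conclusion.** The concern holds as a gap between a stopping rule and the tests required to apply it. For an asymptomatic participant with baseline ALT/AST <1.5×ULN, ALT/AST >3 to <5×ULN, TBL <2×ULN and ALP <3×ULN, INR is the only 7.1.1 ground available, and no required test measures it. For baseline ≥1.5×ULN the first required INR comes at 3 times baseline, with the other limbs as partial cover above 5×ULN.

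This conclusion rests on the protocol text alone. The size in people does not: there is no event rate, the 1 to 6 participants is an assumption about band entry, and those with INR >1.5 would be rare and could be none. The correction is still worth making, because it lets a safety rule the sponsor already wrote be applied, at little cost.

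**What to change.** In Section 8.2.7.1, add a clause requiring PT-INR (the Hepatic Coagulation Panel in Section 10.5) with the 48-to-72-hour repeat whenever ALT or AST is >3×ULN. The clause should carry its own trigger, because for baselines above 1.5×ULN the repeat panel starts only at 2 times baseline, which is later than the 7.1.1 threshold. It should not apply to isolated ALP or TBL elevations, which also start the repeat panel but cannot meet the INR limb.

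The cost is one clause in a protocol amendment, with IRB/IEC approval and best bundled with other changes, and one added blood test in the few participants above 3×ULN. Some of those will have a high baseline and a small rise: from 2.9 to 3.05×ULN is about 5% (3.05/2.9 = 1.05). The central laboratory already offers the test, and no interruption threshold or analysis changes.

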8.3. Adverse Events, Serious Adverse Events, and Product Complaints

The definitions of the following events can be found in section [10.3](#) Appendix 3:

- Adverse events (AEs)
- Serious adverse events (SAEs)
- Product complaints

These events will be reported by the participant (or, when appropriate, by a caregiver, surrogate, or the participant's legally authorized representative).

The investigator and any qualified designees are responsible for detecting, documenting, and recording events that meet these definitions and remain responsible for following up events that are serious, considered related to the study intervention or study procedures, or that caused the participant to discontinue the study intervention or study (see Section [7](#)).

Care will be taken not to introduce bias when detecting events. Open-ended and non-leading verbal questioning of the participant is the preferred method to inquire about event occurrences.

After the initial report, the investigator is required to proactively follow each participant at subsequent visits/contacts. All SAEs and AEs of special interest (as defined in Section [8.3.4](#)) will be followed until resolution, stabilization, the event is otherwise explained, or the participant is lost to follow-up (as defined in Section [7.3](#)). For product complaints, the investigator is responsible for ensuring that follow-up includes any supplemental investigations as indicated to elucidate the nature and/or causality. Further information on follow-up procedures is provided in section [10.3](#) Appendix 3.

